4.4.4. Vital Signs and Physical Examination

The actual value and change from baseline to each on-study evaluation and to the last on study evaluation will be summarized for vital signs based on Safety Population.

A summary table of the number and percent of patients with treatment-emergent potentially clinically significant (PCS) vital signs parameters will be tabulated based on the following criteria:

Variable Name	PCS – Low If:		PCS – High if:	
	Observed Value is:	Decrease from Baseline is:	Observed Value is:	Decrease from Baseline is:
Systolic Blood Pressure	<90 mmHg	≥ 20 mmHg	>180 mmHg	≥ 20 mmHg
Diastolic Blood Pressure	<50 mmHg	≥ 10 mmHg	>105 mmHg	≥ 10 mmHg
Heart Rate	<50 bpm	≥ 25 bpm	>120 bpm	≥ 15 mmHg

All tables summarizing vital sign measurements only include visits in which at least 10% of the analysis population had measurements. Vital sign measurements will be presented for each patient in a data listing.

All physical examination findings will be presented in data listings.

4.4.5. Electrocardiogram

Actual value and change from baseline will be summarized by visit over time for heart rate, QT interval, and QTc interval; continuous summary statistics will be based on the mean ECG values at each timepoint, if appropriate. All tables summarizing ECG measurements only include visits in which at least 10% of the analysis population had measurements.

Based on the 12-lead ECG results, the number and percentage of patients whose mean QTc value at any point meetings any of the following categories will be summarized:

- >450 msec
- >480 msec
- >500 msec
- increase from baseline >30 msec
- increase from baseline >60 msec

Electrocardiogram and echocardiogram/MUGA data for each patient will be provided in data listings.

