11.7 Electrocardiograms

All patients will have a 12-lead ECG performed during screening.

For patients with MF in Stage 2, during days when pharmacokinetic (PK) samples are drawn (C1 and C2, Infusion 1), an ECG will be performed at 3 distinct time points (triplicates) within 5 minutes (\pm 5 minutes) prior to selected PK sample collections as follows: pre-infusion, and at 30 and 60 minutes post-infusion. An ECG should be performed after the patient is supine for 5 minutes.

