4.4.3. Laboratory Data

Clinical laboratory values will be expressed in Système International (SI) units and tabulations will be based on Safety Population.

The actual value and change from baseline (Day 1) to each on-study evaluation through cycle 6 will be summarized for each clinical laboratory parameter, including hematology, clinical chemistry, coagulation, and urinalysis. In the event of repeat values, the last non-missing value closest to the planned study day/time will be used. Box plots will also be presented.

Shift tables of change in CTCAE grade of laboratory parameters from baseline to worst value and from baseline to last value on study will be presented for each disease. Both scheduled and unscheduled visits will be included in shift tables.

To assess for possible drug-induced liver injury (DILI) (FDA 2009), alanine aminotransferase, aspartate aminotransferase, and total bilirubin results will be listed for patients that meet Hy's law criteria. Hy's Law case candidates are defined as subjects with peak ALT or AST $>3 \times$ upper limit of normal (ULN) and total bilirubin $>2 \times$ ULN within ± 7 days.

All laboratory data will be provided in by-patient data listings.

By-patient listings will also be presented for all laboratory values with CTCAE Grade ≥ 3 and for all clinically significant laboratory values with CTCAE Grade ≥ 3 .

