Table 7-3 Stage 3A: Study Events Schedule for Screening and Cycles 1-4 for Patients with CMML

Procedures	Day -28 to 0	Days 1-3 (Up to Day 10 if Infusion(s) Held) Tagraxofusp Treatment		Cycle 1 Day 8±3 ¹	Day 21±3 ²	Day 28±3, Then Every 7±3 days (Only if Delayed End of Cycle: for Toxicity Resolution)
		Screening	Pre-Infusion	Tagraxofusp Infusion		
Informed consent form ³	X					
Inclusion/exclusion criteria ³	X					
Medical history	X					
12-lead ECG	X					
ECOG performance status	X	X (Infusion 1, C1)			X	X
Physical examination, including assessment for hepatomegaly and splenomegaly	X			X	X	
Pregnancy test ⁴	X					
Vital signs and weight ⁵	X	X	X	X	X	X
MUGA scan or 2-D Echocardiogram ⁶	X					
Hematology ⁷	X	X		X	X	X
Serum chemistry ⁸	X	X		X	X	X
Coagulation parameters: PT/INR, aPTT ⁹	X	X		X	X	X
Peripheral blood for flow cytometry	X	X (Infusion 1)		X		
Peripheral blood for IL-10 testing		X (Infusion 1, C1)			X C1 and C4	
Peripheral blood for translational studies (select centers)		X (Infusion 1, C1)			X C1 and C4	
Bone marrow aspiration/biopsy ¹⁰	X				X C1 and C4 ¹¹	
MRI or CT for assessment of hepatomegaly and splenomegaly ¹²	X				X C1 and C4 ¹¹	
Immunogenicity sampling ¹³		X (Infusion 1)			X	

Procedures	Day -28 to 0	Days 1-3 (Up to Day 10 if Infusion(s) Held) Tagraxofusp Treatment		Cycle 1 Day 8±3 ¹	Day 21±3 ²	Day 28±3, Then Every 7±3 days (Only if Delayed End of Cycle: for Toxicity Resolution)
		Screening	Pre-Infusion			
Cytogenetic and molecular genetic testing	X				X C1 and C4	
Administration of premedications ¹⁴		X				
Tagraxofusp administration ¹⁵				X		
MPN-SAF TSS evaluation ¹⁶	X				X	
Baseline/tumor response assessment ¹⁷	X				X C1 and C4 ¹¹	
Vision assessment	X				X	
Prior/concomitant medications/therapies (including concomitant platelet and RBC transfusions)	X	X	X	X	X	X
AE and SAE monitoring	X	X	X	X	X	X

AE = adverse event; aPTT = activated partial thromboplastin time; CT = computed tomography; ECG = electrocardiogram; ECOG = Eastern Cooperative Oncology Group; INR = international normalized ratio; MPN-SAF TSS = Myeloproliferative Neoplasm Symptom Assessment Form Total Symptom Score; MUGA = multigated acquisition; PT = prothrombin time; SAE = serious adverse event.

- 1 Day 8 visit is required for C1 only and must be performed at the site.

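### The 10% visit rule in SAP 4.4.4 and 4.4.5 can keep sparse readings out of the vital-sign outlier table, and arguably the QTc one; separately, Stage 3A schedules no on-treatment ECG

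*SAP*

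**What the plan says.** **Vital signs (SAP 4.4.4).** By-visit values and changes come first, then the outlier table: "A summary table of the number and percent of patients with treatment-emergent potentially clinically significant (PCS) vital signs parameters will be tabulated". The next statement is: "All tables summarizing vital sign measurements only include visits in which at least 10% of the analysis population had measurements". Neither outlier tables nor unscheduled readings are exempted.

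**ECG (SAP 4.4.5).** The first paragraph covers by-visit summaries and ends: "All tables summarizing ECG measurements only include visits in which at least 10% of the analysis population had measurements". A new paragraph then counts "the number and percentage of patients whose mean QTc value at any point" meets one of five categories: above 450, 480 or 500 msec, or an increase from baseline above 30 or 60 msec.

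**Laboratory (SAP 4.4.3).** For shifts from baseline to worst and to last value, the rule is the opposite: "Both scheduled and unscheduled visits will be included in shift tables".

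**Visit labels and percentages.** SAP 3.11 tabulates data under the visit recorded on the eCRF and gives no rule for grouping unscheduled readings. SAP 3.2 and 3.10 call for a missing-data category in categorical summaries, and 3.10 keeps patients with missing results in the percentage denominator.

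**Schedule.** Protocol 11.7 says: "All patients will have a 12-lead ECG performed during screening". It schedules on-treatment ECGs only for MF patients in Stage 2. Protocol Tables 4 and 5 and SAP Tables 7-3 and 7-4 agree: Stage 3A has one ECG, at screening. SAP Table 7-3 also has a column headed "Then Every 7±3 days (Only if Delayed End of Cycle: for Toxicity Resolution", at which vital signs are taken.

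**The concern.** A minimum-attendance rule is sensible for means by visit, where a handful of patients gives an unstable summary. An outlier table has a different job: to count every patient who ever had an extreme value. Extreme values are more likely at sparsely attended visits, such as an extra visit because the patient is unwell, a delay visit for toxicity, or a late cycle that few patients reach. If those visits are removed first, the count can only fall.

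The readings at stake are relevant here. Protocol 8.2.3.1 lists hypotension among the signs of capillary leak syndrome (CLS) and places onset 3 to 8 days after treatment starts. The Day 8 visit is required in Cycle 1 only. From Cycle 2, unless infusions are held, no vital-sign visit is scheduled between the dosing days and the end of the cycle. A low blood pressure in that interval would normally come from an unscheduled visit.

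The second issue is separate. SAP 3.5 gives Stage 3A its own safety column, and Protocol 5.1 names ECGs as a safety assessment. A QTc-increase row in that column would have no scheduled on-treatment data behind it, and a reader could take a zero as reassurance.

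**Working it through.** The plan states no figure to reproduce. The check sets the wording against the schedule and converts 10% into patients.

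1. **Reach of the rule.** In 4.4.4 the sentence refers to all vital-sign tables and follows the PCS table, so the PCS table is covered. In 4.4.5 the sentence closes the by-visit paragraph and comes before the QTc category table. Its literal scope still takes in that table, but the category table has its own scope, at any point. The two conflict and the SAP does not say which prevails.

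2. **Patients needed for a visit to be kept.** For an analysis population of N this is 0.10 × N, rounded up. The SAP does not say whether the analysis population is the whole Safety population or each column. Stage 3A was planned at about 20 per cohort, about 40 in all (SAP 3.1.2), but enrolment was stopped (SAP 5) and the actual N is not given. The values below are therefore assumptions.

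| N (assumed) | Patients needed | Largest number dropped |
|---|---|---|
| 10 | 1 | 0 |
| 11 | 2 (1.1 rounded up) | 1 |
| 20 | 2 | 1 |
| 40 | 4 | 3 (3/40 = 7.5%) |
| 100 | 10 | 9 |

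A lone reading is 1/10 = 10% at N = 10 and is kept. It is 1/11 = 9.1% at N = 11 and is dropped, as it is at every larger N.

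3. **Chance that a sparse visit survives.** Suppose each patient independently has probability p of a reading under that visit label. The visit is kept with probability P(X ≥ patients needed), where X is Binomial(N, p).

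| p (assumed) | N = 20 | N = 40 |
|---|---|---|
| 0.025 | 8.8% | 1.7% |
| 0.05 | 26.4% | 13.8% |
| 0.075 | 44.9% | 35.3% |

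These figures assume separate visit labels. If all unscheduled readings share one label, that label may reach 10% and nothing is lost.

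4. **Stage 3A QTc.** Scheduled post-baseline ECGs per patient: 0. Let m be the number with any unscheduled on-treatment ECG. With all N patients in the denominator, an increase row cannot exceed m/N. With m = 0 it reads 0/40 = 0%. With m = 3 of 40 it cannot exceed 3/40 = 7.5%, even if all three patients had an increase. Removing the 10% rule leaves the number of scheduled on-treatment ECGs at 0.

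**The case against.** The strongest answer is that nothing is lost. All vital signs and ECGs appear in by-patient listings. Findings that need intervention or further investigation are adverse events under Protocol 13.1.1, and SAP 4.4.2 tabulates adverse events whatever the visit. CLS has its own summaries in 4.4.2.1. Vital signs are also scheduled around every infusion, at Cycle 1 Day 8 and at the end of each cycle. This stands, and it confines the harm to the summary incidence tables. It does not correct those tables: a listing does not repair an undercount.

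For ECGs, the specific wording (at any point) can fairly be read as overriding the general rule. That stands too, so the QTc part is an ambiguity to resolve rather than a demonstrated exclusion. The vital-sign part does not have this escape.

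A reader might infer that Stage 3A will show no QTc prolongation by construction. The documents do not support that. The rows above 450, 480 and 500 msec are not limited to post-baseline values, so a high screening QTc could fill them. An unscheduled ECG could still count in the increase rows if at any point prevails, if a shared label reaches 10%, or if the relevant population is 10 or fewer. The missing-data category, if applied to this table, would show unmeasured patients as missing. Because 3.10 also leaves those patients in the denominator, the caution about a low percentage remains.

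**Conclusion.** The point holds as a fault in how summary safety tables are specified. Followed as written, SAP 4.4.4 can leave readings from unscheduled, toxicity-delay or late-cycle visits out of the PCS counts, and 4.4.5 may do the same for QTc, while 4.4.3 takes the opposite approach for laboratory values. Any resulting bias in counts of extreme values is downward. Its size cannot be fixed from the documents: it depends on the actual N, on what the analysis population means and on how unscheduled readings are labelled. The figures of 4 patients at N = 40 and 2 at N = 20 are illustrations.

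The Stage 3A QTc gap is a separate matter that comes from the protocol's ECG schedule, and it should not be attributed to the 10% rule. Its consequence is limited but definite: a low or zero percentage with a QTc increase in that column would not show that QTc was unaffected. I make no claim about CMML patients in Stage 2, because Protocol 5.1 keeps those enrolled under Amendment 6 or earlier on that amendment's schedule, which the documents do not reproduce.

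The study is descriptive and uncontrolled and has full listings, so this is worth correcting but does not threaten its main conclusions.

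**What to change.** - In SAP 4.4.4 and 4.4.5, limit the 10% rule to by-visit descriptive statistics, and say whether the percentage refers to the whole Safety population or to each column.
- Build the PCS and QTc category tables from every reading after the first dose, scheduled or unscheduled, in line with 4.4.3. This also stops a screening QTc from being counted in the absolute rows.
- For the increases above 30 and 60 msec, use as denominator the patients with a baseline and at least one post-baseline ECG, and print that number.
- Label Stage 3A QTc as not systematically assessed on treatment, and list any unscheduled ECGs.

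The cost is SAP wording and a little programming, with no new patient procedure. Outlier counts may rise slightly, and the report must state the Stage 3A limitation openly.

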4.4.6. Concomitant Medications

Concomitant medications will be coded using the WHO Drug Dictionary, version September 2016. Results will be tabulated by anatomic therapeutic class (ATC) and PT.

Concomitant medications will be tabulated where any medications that were not discontinued prior to first dose of study drug and those started after the first dose of study treatment will be included. If an end date is missing or the medication is ongoing, the medication will be considered concomitant.

The use of concomitant medications and subsequent treatment(s) will be included in by-patient data listings.

Prior systemic therapies for MPN will also be summarized by ATC and PT.

4.5. Summary of Immunogenicity Parameters

Immunogenicity parameters will be summarized as described in [Section 3.5](#).

Analyses will be conducted in accordance with the principles outlined in ([Shankar, et al. 2014](#)) and will include:

- Incidence of patients with positive anti-drug antibodies, specific anti-hIL-3 antibodies, and neutralizing antibodies will be assessed by cycle uniquely through cycle 6 and cycles >6 , collectively. Incidence will be summarized by number and percent of patients with positive antibody results.
- Mean fold increase from baseline and geometric mean titer are tabulated by scheduled assessments. Summary statistics will include mean, standard deviation, median, min, and max.
- Incidence of patients with a ≥ 10 fold increase in anti-drug antibody titer and/or a ≥ 4 fold increase in anti-hIL-3 antibody titer will be tabulated.

Immunogenicity parameters will be included in by-patient data listings.

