2. PATIENT POPULATION

2.1. Population Definitions

The following patient populations will be evaluated and used for presentation and analysis of the data for all trial stages:

- Modified Intent-to-Treat (mITT) Population: All patients who are eligible based on the screening criteria who received at least 1 dose of tagraxofusp and are evaluable for efficacy (has an efficacy assessment after first treatment or discontinued due to death or progressive disease) prior to that time. Patients will be grouped according to the planned dose level at time of enrollment.
- Per-Protocol (PP) Population: All patients from the mITT population who are compliant with all major aspects of the protocol and have received at least 1 cycle of tagraxofusp (or treatment was delayed or patient discontinued treatment early due to safety finding related to study treatment). Patients will be grouped according to the planned dose level at time of enrollment.
- Immunogenicity Population: All patients enrolled in the study who received at least 1 dose of tagraxofusp and had at least 1 non-missing immunogenicity sample result.
- PK Population: All subjects who receive at least 1 dose of Tagraxofusp, have at least one plasma sample collected, and the corresponding plasma PK concentration is quantifiable.
- Safety Population: All patients enrolled in the study who received at least 1 dose of tagraxofusp. Patients will be grouped according to the actual dose level received.

The mITT population is the primary population for the analysis of efficacy parameters, and will be used to support baseline endpoints. The immunogenicity population will be used for summary of immunogenicity results. The PK population will be used for the analysis and summary of PK data. The Safety population is the primary population for the analysis of disposition, baseline, and safety endpoints. Patients included in the PP population or reasons for exclusion from the PP population will be identified in a data listing. Note that the intent-to-treat population, defined as all eligible patients, will not be used in any analyses.

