- 10 Morphology and WBC differential/blast count on aspirate. Baseline must be performed within 28 days prior to the first administration of tagraxofusp. Subsequent bone marrow aspirates and biopsies will be performed at the end of C1 and C4 and then every 12 weeks (± 7 days) thereafter. Bone marrow evaluation should also be performed at End of Treatment including patients who discontinue study therapy prior to completion of C4; if a bone marrow evaluation was performed within 4 weeks prior to the end of treatment, a repeat evaluation does not need to be performed at this time, unless clinically indicated.
- 11 Bone marrow aspirate and imaging studies are to be repeated at the end of C1 and C4 and then every 12 weeks (± 7 days) thereafter.
- 12 A baseline MRI or CT scan must be performed within 28 days prior to the first administration of tagraxofusp. Subsequent imaging studies will be performed at the end of C1 and C4 and then every 12 weeks (± 7 days) until there is evidence of relapsed or progressive disease. Abdominal scan is required; evaluation of chest/pelvis may be obtained at the Investigator's discretion. Scan must include measurement of spleen and liver volume. Subsequent to Week 24, for patients receiving ongoing therapy (or those who discontinue therapy but are without evidence of PD and continue to be evaluated in ongoing follow-up) the frequency of imaging studies may be reduced (obtained less frequently) if peripheral blood and/or clinical assessments indicate clinical stability, as per the Investigator's discretion, in consultation with the Medical Monitor. Imaging should also be performed at End of Treatment, including patients who discontinue study therapy prior to completion of C4; if a imaging was performed within 4 weeks prior to the end of treatment, a repeat evaluation does not need to be performed at this time, unless clinically indicated. Whenever clinically feasible, it is strongly requested that the same imaging modality (MRI or CT) at both baseline and subsequent timepoints be utilized for any given patient throughout their evaluation on-study.
- 13 Peripheral blood (serum) samples (10 mL) will be collected for the detection of tagraxofusp reactive antibodies on Day 1 (pre-infusion) and Day 21 (the end of cycle collection may also serve as the pre-infusion collection for the subsequent cycle).

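### SAP 4.5 labels by-cycle antibody positivity as incidence, so patients positive before the first dose count as incident and the table shows prevalence rather than drug-induced immunogenicity

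*SAP*

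**What the plan says.** SAP 4.5 plans three kinds of immunogenicity summary.

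- **Positivity.** For anti-drug, anti-hIL-3 and neutralizing antibodies, incidence "will be assessed by cycle uniquely through cycle 6", with later cycles pooled. The counting rule is: "Incidence will be summarized by number and percent of patients with positive antibody results".
- **Titer.** "Mean fold increase from baseline and geometric mean titer are tabulated by scheduled assessments".
- **Fold rise.** "Incidence of patients with a ≥ 10 fold increase in anti-drug antibody titer and/or a ≥ 4 fold increase in anti-hIL-3 antibody titer" is to be tabulated.

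The section opens with a general reference to a published immunogenicity reporting paper ("Analyses will be conducted in accordance with the principles outlined in" that paper), but it does not write out that paper's categories.

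Four other places bear on this:

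- SAP Table 7-3, footnote 13, has samples drawn for "tagraxofusp reactive antibodies on Day 1 (pre-infusion) and Day 21". Protocol 11.13 gives the same timing for Cycles 1 to 4. Cycle 1 therefore contains one sample taken before any drug and one taken after.
- SAP 2.1 defines the Immunogenicity Population as patients who "received at least 1 dose of tagraxofusp and had at least 1 non-missing immunogenicity sample result". The timing of that result is not restricted.
- SAP 3.5 lays out the immunogenicity tables by dose and disease, with no split by baseline antibody status.
- SAP 4.6 breaks down the PK summaries by baseline ADA titer, so the SAP itself allows for titers before treatment.

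**The concern.** Incidence of anti-drug antibody is normally read as what treatment produced: patients who turn positive on drug, plus those whose existing antibody is boosted. The positivity rule in SAP 4.5 asks only whether a result is positive. A patient positive before the first infusion, and still positive later, would appear as incident in each cycle without the drug having done anything.

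The baseline-relative summaries might have supplied the missing information. However, a fold increase needs a baseline titer, and the SAP does not say what titer a negative sample receives. The one count that looks at change is therefore not fully defined for patients who start negative, and those are the patients in whom new antibody would appear.

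At stake is how the study report describes immunogenicity. SAP 1.1.3.2 lists it among the secondary objectives carried from protocol Amendment 6 and earlier. As planned, no table separates antibody that was already there from antibody that arose or rose on treatment.

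**Working it through.** The documents give no antibody rate, sample size or target for immunogenicity, so there is no figure to reproduce. The check is a reading of the rules followed by an identity on assumed rates.

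**Reading the rules together.** The numerator in SAP 4.5 is any positive result. SAP 3.4 defines baseline for all analyses, but the positivity rule does not refer to it. SAP 3.11 tabulates data under the visit recorded on the eCRF, so a pre-infusion sample recorded under Cycle 1 falls in Cycle 1 by default. Elsewhere the SAP writes a treatment-emergent condition where it wants one: adverse events in 4.4.2 and vital signs in 4.4.4. Section 4.5 has none.

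**Inputs (all assumed, none in the documents).**

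- q: share of patients positive at baseline, 0 to 90%
- t: share of baseline negatives who seroconvert, 50% or 90%
- b: share of baseline positives meeting the fold-rise threshold, 25%, 75% or 100%

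**Formulas.** These take baseline positives to stay positive. In Cycle 1, if the pre-infusion sample is counted, that is not needed.

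- Any positive = q + (1−q)t
- Treatment-emergent (induced + boosted) = (1−q)t + qb
- Excess = q + (1−q)t − (1−q)t − qb = q(1−b)
- Fold-rise count if baseline negatives are left out = qb, which misses (1−q)t

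| q | t | b | Any positive | Treatment-emergent | Excess (points) | Fold count, negatives left out | Missed (points) |
|---|---|---|---|---|---|---|---|
| 0 | 50% | 25% | 50% | 50% | 0 | 0 | 50 |
| 25% | 50% | 25% | 62.5% | 43.75% | 18.75 | 6.25% | 37.5 |
| 50% | 90% | 75% | 95% | 82.5% | 12.5 | 37.5% | 45 |
| 50% | 90% | 100% | 95% | 95% | 0 | 50% | 45 |
| 90% | 50% | 25% | 95% | 27.5% | 67.5 | 22.5% | 5 |

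Over the whole assumed grid the excess runs from 0 to 67.5 points (0.90 × 0.75). The amount missed if negatives are left out runs from 5 (0.10 × 0.50) to 90 points (1.00 × 0.90).

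**The negative-baseline convention.** If a negative sample is given a minimum titer m, the rule can be computed. A seroconverter counts at a post-dose titer of at least 10m for anti-drug antibody or 4m for anti-hIL-3. With m = 10 these are 100 and 40; with m = 50 they are 500 and 200. SAP 4.5 does not state whether negatives are left out or given a titer, nor the value of m. SAP 3.10 says only that, in general, missing data points are not substituted.

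**A small worked case (assumed counts).** Take 20 patients, 18 negative and 2 positive at baseline. Fifteen of the 18 seroconvert and 1 of the 2 is boosted.

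- Treatment-emergent: (15 + 1)/20 = 80%
- Any positive: (15 + 2)/20 = 85%, an excess of 5 points = 0.10 × (1 − 0.50)
- Fold-rise count with negatives left out: 1/20 = 5%

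When few are positive at baseline, the positivity table is close to the treatment-emergent figure and the fold-rise count is the fragile one. When many are, the positivity table is the one that drifts.

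**Denominator.** SAP 2.1 admits a treated patient whose only result is pre-dose and who cannot be seen to turn positive. It also admits one with no baseline result, who cannot be classed as induced or boosted. If the general rule in SAP 3.10 applies here, with percentages taken over the total population including missing results, later-cycle percentages also fall as patients stop being sampled.

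**The case against.** The strongest reply is that much of this is silence rather than a wrong rule. SAP 4.5 invokes a reporting paper that may define the categories. Baseline is defined for all analyses. Table shells are kept in a separate document (SAP 9) and might include a baseline row. Protocol 14.6 places the immunogenicity analyses in separate SAPs. By-patient listings would allow re-derivation. Immunogenicity is not among the Stage 3A objectives, the remaining analyses are descriptive (SAP 5), and no decision depends on this table.

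Part of this stands. A reader might infer that the fold-rise rule excludes patients negative at baseline. It does not; the text leaves their value undefined, and a minimum titer would make the rule work. A reader might also infer that seroconverters are lost. They are not; they appear in the positivity table, mixed with patients who were already positive. Counting the Cycle 1 pre-infusion sample is the default reading, not an explicit instruction. A claim that immunogenicity is misreported in both directions goes beyond the documents, which give no antibody rates and do not say which antibodies are common or rare before treatment. The population point matters only for treated patients lacking a baseline or post-dose result; with sampling each cycle, at end of treatment and 30 days after the last infusion, they may be few.

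The rest does not rescue the rule. The positivity rule is explicit and carries no baseline condition, and a general citation does not tell a programmer which samples, denominator or negative titer to use. SAP 1.1.3 makes this document the basis for the study report, and it points to no separate immunogenicity plan. Listings permit reconstruction afterwards, but they are not a prespecified summary.

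**Conclusion.** The point holds as a defect of definition. As written, the by-cycle table in SAP 4.5 measures prevalence of positivity under the name of incidence. It exceeds treatment-emergent incidence by q(1−b) if baseline positives stay positive. The excess is zero if no patient is positive at baseline or all baseline positives are boosted, and it reaches 67.5 points at the extreme of the assumed ranges. These sizes are illustrative, and the actual discrepancy cannot be stated from the documents.

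The fold-rise count is not reproducible until the value for a negative baseline is fixed, and the Immunogenicity Population does not guarantee that a patient can be classified. This is a risk of misstatement, not a demonstrated one. It is worth correcting because the correction is cheap and the intended quantity cannot be read from any planned table.

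**What to change.** In SAP 4.5:

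1. Report baseline prevalence for each antibody from the pre-first-dose sample, in its own row.
2. Report treatment-emergent incidence as treatment-induced (negative at baseline, positive at any post-dose sample) plus treatment-boosted (positive at baseline with the fold rise the SAP already states for that antibody), showing the two parts separately. The SAP gives no fold threshold for neutralizing antibody, so either add one or report only the induced part.
3. Use as denominator the patients with a baseline result and at least one post-dose result.
4. State the minimum titer assigned to negative samples in fold calculations.
5. Keep the by-cycle positivity table, label it prevalence, and state its denominator.
6. If a separate immunogenicity plan exists, cross-reference it and align the definitions.

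The cost is SAP wording and programming on samples already scheduled, with no new assays. The small downside is that patients without a baseline or post-dose sample leave the incidence denominator, so their number should be shown separately.
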